4.3.1 Masking and Randomization Methodology

Eligible subjects will be randomized in a 1:1:1:1 ratio to receive TRS01 [REDACTED], TRS01 [REDACTED], TRS01 [REDACTED] % or vehicle dose on Day 1.

Randomization will occur after subjects meet all eligibility requirements at Screening and Day 1/Visit 3 (1-day post-surgery). Each subject will be assigned a unique subject number.

Each kit package (containing two IP bottles) will contain a kit number that can be later correlated to the subject number at the site.

Randomization for the US sites will be separate from the French site.

The randomization codes and all data sets will be stored in a secure area accessible only to delegated study personnel and only released on completion of the study and after the study database has been locked.

In this study all parties are to be masked to the allocated treatment; investigators, study staff and subjects. At the site, there will be designated unmasked study staff that will train the subject on all study procedures related to IP administration.

In emergency situations for reasons of subject safety (e.g. serious unexpected /unlisted drug related event; medical emergency; potentially life-threatening drug interaction) the masking code may need to be broken. In those cases, whenever possible, a request for unmasking should be discussed with the sponsor (or designee) prior to unmasking. Detailed instruction on the method for breaking the mask will be provided during site training and noted in the Investigator study file.

Following the first IP administration, if the subject perceives any AE that may be attributed to the IP, these should be reported to the unmasked site personnel.

4.4 INFORMED CONSENT

Prior to undergoing any study-related activity, the Principal Investigator or his/her designee will discuss the purpose and pertinent details of the study with each potentially eligible subject. The explanation will be sufficiently detailed to allow the subject to make an informed decision to participate in the study. If the subject is willing to participate in the study, he/she will be requested to give written informed consent. A copy of the Informed Consent Form (ICF) will be signed by both the subject and the Principal Investigator or his/her designee.

The signed and dated ICF will be retained with the study records, and a copy of the signed and dated ICF will be given to the subject.

5 STUDY ASSESSMENTS

5.1 TIMING OF STUDY ASSESSMENTS

All procedures will be performed according to the following schedule unless otherwise specified. See also the summary of assessments in Appendix 1 that outlines this schedule in tabular form. Note: [REDACTED]

5.1.1 Visit 1: Screening (Day (-30) to Day (-1)).

This visit is a period where assessments can be collected. Ocular assessments are to be performed on both eyes.

- Signed and dated informed consent
- Demographic information including iris color
- Medical and Ophthalmic History
- Inclusion/exclusion criteria
- Concomitant Medications
- Urine pregnancy test (if female of child-bearing potential)
- Snellen Distance Visual Acuity (VA) by Pinhole Method
- Slit-lamp biomicroscopy
- Intraocular pressure by Goldmann Applanation Tonometry
- Dilated Ophthalmoscopy
- Self-administration eye drop assessment (self-administration/care provider administration of “artificial tear eye drop”)
- Assessment of adverse events

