14. Have current or history of prior ocular inflammation in the study eye not related to prior allowed surgical procedure.
15. In the opinion of the Investigator, have current clinically significant dry eye requiring therapy of greater than twice a day (BID) eye drops in the study eye. Use of PRN artificial tears up to twice a day is allowed and should not be dosed within 10 minutes of investigational product dosing.
16. Use any Cannabidiol products during the trial.
17. Have history of glaucoma or uncontrolled IOP >22 mmHg in the study eye on day of screening.

18. Have floppy iris syndrome noted for the contralateral eye prior to surgery in the study eye.
19. Have any clinically significant systemic disease or condition (e.g. hematological diseases) that, in the Investigator's opinion, may confound the trial results, pose a safety risk to the subject or preclude the subject from adhering to the protocol or completing the trial per protocol and installing eye drops.
20. Have a known history of alcohol and/or drug abuse.
21. Be an employee of the site that is directly involved in the management, administration, or support of this study or be an immediate family member of the same.
22. Have been exposed to an investigational drug or investigational medical device within 60 days prior to Visit 1.
23. Be pregnant or lactating.

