4.3 RANDOMIZATION INCLUSION CRITERIA

To qualify for randomization at the Day 1 (Visit 3), a subject must:

1. Have undergone routine, uncomplicated cataract surgery (phacoemulsification or extracapsular extraction) with posterior chamber IOL implantation, not combined with any other surgery (including but not limited to use of iris retractors, capsular fixation ring or anterior capsule staining with dye). Specifically, have NOT had any cataract surgery complication such as a posterior capsular rupture, vitreous loss or significant iris damage.
2. Have an IOP of \leq 30 mmHg. Notes: Fluid release from the anterior chamber through the surgical incision is allowed (manual burping). The final IOP post release of fluid must be \leq 30 mmHg and will be recorded as the visit IOP value. Use of IOP lowering medications are allowed beginning on Day 0, with the exception of prostaglandins. IOP lowering eye drops should be dosed at least 30 minutes before investigational product dosing.
3. Have anterior chamber cells \geq grade 2.
4. Continue to meet inclusion/exclusion criteria with respect to current ocular and medical conditions and must not be taking prohibited medications (section 6.4).

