5.1.2 Visit 2: Day 0 – Surgery

This visit will occur no more than 30 days and no less than 1 day after Visit 1 and the following will be performed/assessed:

- Concomitant medication update
- Occurrence of any AEs since the last visit
- Routine pre-surgical care and procedures as determined by the Investigator

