5.1.3 Visit 3: Day 1 (1-day post-surgery)

This visit should be scheduled to occur in the morning, if possible, to allow for QID dosing on Day 1 for randomized subjects. Perform the following assessments. Ocular assessments are to be performed on both eyes, unless otherwise noted:

- Subject-Rated Ocular Pain Assessment – prior to any other assessments
- Assessment of adverse events following subject rated ocular pain assessment. Changes that are expected due to uncomplicated cataract surgery will not be classified as AEs but will be recorded.
- Concomitant medication update
- Snellen Distance VA by Pinhole Method
- Slit-lamp biomicroscopy
- Intraocular pressure by Goldmann Applanation Tonometry
- Randomization: subjects that meet eligibility criteria ([section 1](#)) should be randomized to one of the treatment groups through the Interactive Web Response System (IWRS).
- [REDACTED]
- Dispensation of IP and Dosing Diary: the subject will receive one bottle from the study kit and will be instructed to self-administer the first drop prior to leaving the clinic, under the supervision of the unmasked personnel. The subject will be instructed to record this first dose and all subsequent doses in the dosing diary.
- 40 minutes \pm 10 minutes post IP administration the subject will be assessed for AEs in both eyes. If any AEs are reported at visit 3 that may be attributed to the IP, these should be handled by the unmasked personnel.
- The subject will be instructed to take the bottle home and administer the IP three more times that day. Following the day of this visit the subject will be instructed to begin using the drops four times a day and to continue for the duration of the study.

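### The pregnancy exclusion has to hold again on Day 1, but the only pregnancy test before dosing is at screening, 2 to 31 days before the first drop

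*Combined protocol and SAP*

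**What the plan says.** Section 4.2 (item 23), like the synopsis, states that a subject may not "Be pregnant or lactating". The list is introduced as applying at Visit 1.

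Eligibility is then looked at again after surgery. Section 4.3, item 4, requires that a subject "Continue to meet inclusion/exclusion criteria with respect to current ocular and medical conditions and must not be taking prohibited medications". Section 4.3.1 is broader: "Randomization will occur after subjects meet all eligibility requirements at Screening and Day 1/Visit 3 (1-day post-surgery". Appendix 1 agrees, with a mark for inclusion/exclusion criteria in the pre-dose column of Visit 3.

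The test itself, "Urine pregnancy test (if female of child-bearing potential", stands in the procedure lists for Visit 1 (5.1.1) and Visit 6/Early Termination (5.1.6). It is not in the lists for Visits 2 to 5 or for unscheduled visits (5.1.2 to 5.1.5 and 5.1.7). Its row in Appendix 1 carries the same two marks.

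On timing, section 5.1.2 says of surgery that "This visit will occur no more than 30 days and no less than 1 day after Visit 1". Visit 3 is one day after surgery, and there the subject "will be instructed to self-administer the first drop prior to leaving the clinic, under the supervision of the unmasked personnel". Section 3.3 has dosing four times a day from Day 1 through Day 14, and section 5.1.5 has the subject withhold drops on the day of Visit 6.

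**The concern.** The plan asks for a criterion to hold on two dates but schedules the matching test before dosing on only one of them. A site that follows section 5.1.3 line by line will re-check eligibility, randomize and give the first dose with no current pregnancy result. A pregnancy that began after the screening test, or was too early for that test to show, would pass the Day 1 check unless the subject knew of it and said so.

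Safety is the primary objective of this Phase I/IIa study, and the protocol itself treats reproductive exposure as something to avoid: it excludes pregnant women, requires contraception, and tests twice. What is at stake is whether one of its own exclusions is confirmed when treatment starts. The randomization, the endpoints and the analysis are not affected.

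**Working it through.** The check is calendar arithmetic on the protocol's own day numbering, which includes a Day 0.

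**Inputs**
- Screening (Visit 1): Day -30 to Day -1 (5.1.1)
- Surgery (Visit 2): Day 0 (5.1.2)
- First dose (Visit 3): Day 1 (5.1.3)
- Dosing: Day 1 through Day 14, four times a day (3.3)
- Visit 6: Day 15 ± 1, that is Day 14 to Day 16 (5.1.6)

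**The plan's own figure.** Longest interval from Visit 1 to surgery: 0 − (−30) = 30 days. Shortest: 0 − (−1) = 1 day. Both match section 5.1.2.

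**Age of the screening test at first dose**
- Longest: 1 − (−30) = 31 days
- Shortest: 1 − (−1) = 2 days

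**Interval between the two scheduled tests**
- Longest: 16 − (−30) = 46 days (45 days to the nominal Day 15)
- Shortest: 14 − (−1) = 15 days

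**First dose to the Visit 6 test.** 15 − 1 = 14 days, or 13 to 15 with the visit window. A full course is nominally 14 × 4 = 56 doses. Since drops are withheld on the day of Visit 6, a completer's second test always follows her last dose.

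**With a repeat test at Visit 3 before randomization.** The interval from last test to first dose becomes 0 days.

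**How many women this could concern.** The documents do not say how many subjects would be of child-bearing potential. Assume 0 to 3 of 60. That is a count of women to whom the test applies, not of pregnancies. As a purely illustrative second assumption, let the chance of conceiving over about one month on contraception be 0.1% to 2%:
- upper end: 3 × 0.02 = 0.06 expected pregnancies
- lower end: 0
- three of the four equally allocated arms are active, so at the upper end 0.06 × 3/4 = 0.045 on active drug

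These figures show only the order of magnitude.

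**The case against.** The strongest case on the other side is that the protocol already has a safeguard covering the interval. Inclusion criterion 7 (4.1) requires adequate contraception, for those of reproductive potential who are sexually active, over the whole study and for two weeks after the last dose. A new pregnancy between screening and dosing would then need contraceptive failure or non-adherence. This stands, and it is why the point is minor. But contraception lowers the chance of pregnancy; it does not confirm on Day 1 that the exclusion is met.

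Other points have some weight:
- Section 4.3, item 4, speaks of current ocular and medical conditions and does not name pregnancy. Section 4.3.1 and the Visit 3 mark in Appendix 1 carry no such limit and support including it. Neither says that the re-check must be by test, and a site could ask the subject. So a reader might infer a contradiction in the protocol, or a Day 1 check that cannot be carried out. The text does not go that far: the criterion can be checked by history, but it is not confirmed by a test.
- Thirty-one days is the longest case. Section 5.1.1 treats Visit 1 as a period, so the test may be as recent as Day -1, and section 5.1.2 leaves room for pre-surgical procedures that could include a local test. Neither is required.
- Detection only after a full course describes completers. Under section 5.2, subjects who withdraw early are asked to complete the Visit 6 procedures, so they would be tested sooner.
- A reader might also infer serious harm to each woman concerned. The documents show no reproductive-toxicity or systemic-exposure information, and composition and dose are redacted, so the consequence is unknown.

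Redaction is not a plausible explanation. The pregnancy-test row in Appendix 1 is legible, is separate from the redacted row, and matches the visit lists.

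**Conclusion.** The concern holds as a minor one. Eligibility is to be met at both Screening and Day 1, yet the only pregnancy test before dosing is at screening, 2 to 31 days before the first dose, and completers are next tested after the last dose. The visit arithmetic is exact and needs no assumption. The conclusion also rests on reading pregnancy as part of the Day 1 re-check, which section 4.3.1 and Appendix 1 support.

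Its practical size is small. On an assumed 0 to 3 women of child-bearing potential among 60, with contraception required, the expected number dosed while pregnant is far below one. It would be wrong to read the 0 to 3 as a number of exposed pregnancies, or to conclude that the plan breaches its own exclusion. The schedule does not confirm by test a criterion that it asks sites to re-check, and that is easily put right.

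**What to change.** Keep the Visit 1 test, because section 4.2 applies the exclusion there. Add a repeat urine pregnancy test for women of child-bearing potential to section 5.1.3 and to the Visit 3 pre-dose column of Appendix 1, with the result available before randomization. Alternatively, place the repeat at Visit 2 before surgery, in section 5.1.2 and the Visit 2 column. Visit 3 brings the interval to first dose down to 0 days. Visit 2 leaves 1 day, but a positive result would come before the subject has surgery under the study's steroid and NSAID restrictions. Section 4.3, item 4, could also name pregnancy, so that sites know it belongs to the Day 1 re-check.

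The cost is one more urine test in a few subjects, one line of text and one mark in the schedule. Dose, endpoints, sample size and analysis stay as they are. The repeat narrows the gap without closing it, since a very early pregnancy may still test negative. Moving the Visit 1 test instead of repeating it is not recommended: it would leave the exclusion untested at Visit 1.

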5.1.2 Visit 2: Day 0 – Surgery

This visit will occur no more than 30 days and no less than 1 day after Visit 1 and the following will be performed/assessed:

- Concomitant medication update
- Occurrence of any AEs since the last visit
- Routine pre-surgical care and procedures as determined by the Investigator

5.1.3 Visit 3: Day 1 (1-day post-surgery)

This visit should be scheduled to occur in the morning, if possible, to allow for QID dosing on Day 1 for randomized subjects. Perform the following assessments. Ocular assessments are to be performed on both eyes, unless otherwise noted:

- Subject-Rated Ocular Pain Assessment – prior to any other assessments
- Assessment of adverse events following subject rated ocular pain assessment. Changes that are expected due to uncomplicated cataract surgery will not be classified as AEs but will be recorded.
- Concomitant medication update
- Snellen Distance VA by Pinhole Method
- Slit-lamp biomicroscopy
- Intraocular pressure by Goldmann Applanation Tonometry
- Randomization: subjects that meet eligibility criteria ([section 1](#)) should be randomized to one of the treatment groups through the Interactive Web Response System (IWRS).
- [REDACTED]
- Dispensation of IP and Dosing Diary: the subject will receive one bottle from the study kit and will be instructed to self-administer the first drop prior to leaving the clinic, under the supervision of the unmasked personnel. The subject will be instructed to record this first dose and all subsequent doses in the dosing diary.
- 40 minutes \pm 10 minutes post IP administration the subject will be assessed for AEs in both eyes. If any AEs are reported at visit 3 that may be attributed to the IP, these should be handled by the unmasked personnel.
- The subject will be instructed to take the bottle home and administer the IP three more times that day. Following the day of this visit the subject will be instructed to begin using the drops four times a day and to continue for the duration of the study.

5.1.4 Visit 4: Day 3 (\pm 1 day) post surgery

Perform the following assessments. Ocular assessments are to be performed on both eyes, unless otherwise noted:

- Subject-Rated Ocular Pain Assessment – prior to any other assessments
- Assessment of adverse events. Changes that are expected due to uncomplicated cataract surgery will not be classified as AEs but will be recorded.
- Concomitant medication update
- Snellen Distance VA by Pinhole Method
- Slit-lamp biomicroscopy
- Intraocular pressure by Goldmann Applanation Tonometry
- [REDACTED]
- Review subject's dosing diary for compliance by unmasked personnel

5.1.5 Visit 5: Day 8 (± 1 day) post surgery

Perform the following assessments. Ocular assessments are to be performed on both eyes, unless otherwise noted:

- Subject-Rated Ocular Pain Assessment – prior to any other assessments
- Assessment of adverse events. Changes that are expected due to uncomplicated cataract surgery will not be classified as AEs but will be recorded.
- Concomitant medication update
- Slit-lamp biomicroscopy
- Snellen Distance VA by Pinhole Method
- Intraocular pressure by Goldmann Applanation Tonometry
- [REDACTED]
- Collect used IP and review subject's dosing diary for compliance by unmasked personnel
- Dispense second bottle of IP from subject's assigned kit by unmasked personnel. Subject should be reminded to withhold dosing on the day of Visit 6.

5.1.6 Visit 6/Early Termination: Day 15 (± 1 day) post surgery

Perform the following assessments. Ocular assessments are to be performed on both eyes, unless otherwise noted:

- Subject-Rated Ocular Pain Assessment – prior to any other assessments
- Assessment of adverse events. Changes that are expected due to uncomplicated cataract surgery will not be classified as AEs but will be recorded.
- Concomitant medication update
- Urine pregnancy test (if female of child-bearing potential)

- Snellen Distance VA by Pinhole Method
- Slit-lamp biomicroscopy
- Intraocular pressure by Goldmann Applanation Tonometry
- Dilated ophthalmoscopy
- [REDACTED]
- Collect used IP and the subject's dosing diary by unmasked personnel
- Confirm study completion

5.1.7 Unscheduled Visits

If at any time during the study, outside of the above scheduled visits, the subject requests or the physician determines the subject should be assessed for retreatment or of an AE, an unscheduled visit may occur. Adverse events and concomitant medications will be recorded and the following assessments should be performed on the study eye (and non-study eye if applicable/necessary.):

- Snellen Distance VA by Pinhole Method
- Slit lamp biomicroscopy
- IOP by Goldmann Applanation Tonometry
- Dilated ophthalmoscopy, if indicated

5.2 WITHDRAWAL CRITERIA / EARLY TERMINATION

Subjects have the right to withdraw from the study at any time, for any reason, without jeopardizing their medical care. Where possible, subjects will be followed for safety and encouraged to return for follow-up visits for any unresolved safety events.

In addition, the Investigator or Tarsius' Medical Officer can discontinue a subject from further study medication administration for other reasons related to the best interest of the subject.

If a subject is discontinued from study medication administration at any point of the Treatment Period, he or she will be encouraged to remain in the study for follow up through Day 15.

The reason a subject discontinued from the study is to be clearly described on the Study Exit electronic case report form (eCRF).

Subjects who withdraw from the study will not be replaced. Subjects who withdraw from the study prior to Visit 6 (Day 15) will be asked to complete all procedures outlined in Visit 6.

6 TREATMENT OF SUBJECTS

6.1 PRIOR AND CONCOMITANT THERAPY

At the Screening visit, medications that were taken within the previous 30 days will be collected. At each study visit thereafter, subjects will be questioned concerning any new medications or changes in their current concomitant medications since their previous study visit.

For all medications, the generic name, indication, route of administration, frequency, dose, start date and end date (if applicable) will be collected.

6.2 PERMITTED MEDICATIONS

Therapy considered necessary for the subject's welfare that does not interfere with the evaluation of the study medication will be permitted to be given at the discretion of the Principal Investigator.

The decision to administer a prohibited medication or treatment would be taken with the safety of the subject as the primary consideration. Whenever possible, the Tarsius Medical Monitor will be notified before any prohibited medications or treatments are administered. The Tarsius Medical Monitor should also be contacted if the permissibility of a specific medication or treatment is in question.

Any subject placed on rescue therapy will discontinue use of the study medication and continue study participation through Visit 6.

Subjects on rescue will be considered treatment failures, but the need for rescue therapy will not be considered an AE. Rescued subjects experiencing an AE at the time of rescue will be followed through stabilization or resolution of the AE or the end of the study (whichever comes last). Rescued subjects should not be withdrawn from the study, but rather followed to resolution of signs and symptoms or until the Investigator has deemed the subject is stable.

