1 INTRODUCTION

Intraocular inflammation is a typical undesirable consequence of intraocular surgery such as cataract surgery. It is manifested principally as conjunctival injection, corneal edema, ciliary flush and aqueous cells and flare. Surgical trauma and phacoemulsification energy activate an inflammatory cascade that ultimately leads to formation of prostaglandins, which results in local vasodilation and increased vascular permeability.

Inflammation may resolve with no treatment in 15-28% of patients. However, inadequately treated inflammation after cataract surgery frequently causes pain, photophobia, increased risk for elevated intraocular pressure (IOP), corneal edema, corneal scarring and cystoid macular edema [Aptel et al., 2017]. Thus, managing and treating postoperative inflammation is an important goal following cataract surgery.

Other ocular inflammatory diseases include, for example, non-infectious uveitis, a potentially blinding condition that is the fifth leading cause of visual loss in the developed world (third leading cause of preventable blindness), has been estimated to account for 10% of all visual impairment in the western world and 10–15% of cases of total blindness [Nussenblatt, 1990; Merida et al., 2015]. Anterior uveitis accounts for approximately 80% of non-infectious uveitis cases in the United States [Thorne et al., 2016].

Uveitis is characterized by an inflammatory process that may be acute, recurrent, chronic or acute-on-chronic. Untreated, recurrent bouts of uveitis eventually lead to tissue destruction from direct inflammation or from complications such as cataract, glaucoma and macular edema.

Topical corticosteroids represent first line treatment for both non-infectious uveitis and postoperative inflammation. In the US, topical corticosteroids are routinely prescribed with four times daily (QID) dosing for at least 2 weeks following cataract surgery [Kim et al., 2019].

The side effects associated with steroid use, significantly limit prolonged treatment. The most common adverse effects of ocular steroids are cataract and elevated IOP which can lead to steroid related glaucoma.

Given the limitations of treatment, there is a need for an effective anti-inflammatory drug that does not have an IOP-elevating effect. Tarsius Pharma has developed a novel therapeutic approach for local prevention and treatment of ophthalmic inflammatory diseases. [REDACTED]

[REDACTED]

[REDACTED]

[REDACTED]

[REDACTED]

[REDACTED]

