3.1 SAFETY ENDPOINTS

The primary safety parameter in this study is the incidence and severity of treatment-emergent and treatment-related adverse events (AEs), both systemic and ocular events in subjects with post-cataract inflammation. Changes that are expected due to uncomplicated cataract surgery will not be classified as AEs but will be recorded.

1. Snellen distance visual acuity (VA) by pinhole method
2. Slit lamp biomicroscopy
3. IOP measurement
4. Dilated ophthalmoscopy
5. Change from baseline (1-day post-surgery) to each post-surgery visit in ocular signs:
 - Conjunctival hyperemia
 - Corneal Edema

All Relevant clinical findings will be recorded in the electronic case report form (eCRF).

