6.3 RESCUE MEDICATION USE

Rescue medications will be administered in cases detailed in [section 7.2.2](#). Rescue therapy will be defined as any treatment that would have a therapeutic effect on inflammation in the anterior segment, other than the IP (e.g., systemic treatment with an immunosuppressant agent, or topical corticosteroids in the study eye), regardless of the purpose of administration and whether it was recorded as a rescue therapy on the eCRF.

Systemic immunosuppressive therapy (e.g., methotrexate, cyclosporine, cyclophosphamide, chlorambucil, mycophenolate mofetil, tacrolimus, azathioprine, or adalimumab) or other therapy considered as a rescue therapy, would be administered based on the Investigator's best judgment and only after discussion with Tarsius' Medical Director. Prior to treatment with rescue medication, the subject should answer the "Subject-Rated Ocular Pain Assessment". Only then, rescue medication can be administered and treatment will be recorded as a rescue therapy in the Medications eCRF.

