7.2 SAFETY VARIABLES

Safety measures include AEs/SAEs and clinical assessments from the slit-lamp biomicroscopy findings, IOP, and dilated ophthalmoscopy findings.

AEs and ocular safety measures to be collected in this study are listed in [Table 4](#).

TABLE 4: OCULAR SAFETY MEASURES

Safety Measure	Note
Slit-lamp biomicroscopy: Lid hyperemia, lid edema, conjunctival hyperemia, chemosis, corneal edema, conjunctival discharge/exudate	The status of each of these biomicroscopy parameters will be rated as 0 = None, 1 = Mild, 2 = Moderate, or 3 = Severe. For each abnormal record, the clinical significance (Clinically Significant or Not Clinically Significant) will also be determined. Slit-lamp biomicroscopy will be performed at all study visits, except Visit 2 (Surgery).
Intraocular pressure	The IOP measurements will be performed by Goldmann applanation tonometry. IOP pressure recorded in mmHg (e.g., 18mmHg). IOP measurements will be performed at all study visits, except Visit 2 (Surgery).
Dilated Ophthalmoscopy: IOL (post-surgery), vitreous haze, retina vessels, macula, optic nerve, cup/disc ratio.	The status of IOL position, macula and optic nerve will be determined as Normal or Abnormal. The cup/disc ratio will be recorded with two decimal points (e.g., 0.80). Dilated ophthalmoscopy will be performed at Visit 1 (Screening) and at Visit 6 (Day 15).

Intraocular Pressure (IOP) – IOP will be measured using Goldmann Applanation Tonometry with a single measurement.

These ocular safety measures will be summarized using descriptive statistics. For continuous ocular safety measures, changes from Baseline (Day 1 / Visit 3) variables will also be summarized descriptively.

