- Event occurring before dosing.
- Event easily explained by uncomplicated cataract surgery
- Event or intercurrent illness due wholly to factors other than investigational product use.

Probable:

- Reasonable temporal relationship with investigational product use.
- Likely to be known reaction to agent or chemical group, or predicted by known pharmacology.
- Event cannot easily be explained by subject's clinical state or other factors.

Definite:

- Distinct temporal relationship with investigational product use.
- Known reaction to agent or chemical group, or predicted by known pharmacology.
- Event cannot be explained by subject's clinical state or other factors.

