9.1.3 Analysis of Efficacy

Efficacy measures will be ACC and flare, as well as Subject-rated Ocular Pain Assessment.

Both Investigator-rated ACC and flare data will be assessed as a change from baseline (Visit 3/Day 1) on Days 3, 8 and 15 and a descriptive comparison of the active treatment groups to the vehicle group will be performed.

The Subject-rated Ocular Pain Assessment will be assessed as a change from baseline (Visit 3/Day1) on Days 3, 8 and 15 and a descriptive comparison of the active treatment groups to the vehicle groups will be performed.

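### No visible safety output counts rescue or worsening of anterior chamber cells or flare by arm, so whether a worsened and rescued eye reaches the tabulated AE comparison depends on two investigator judgements

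*Combined protocol and SAP*

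**What the plan says.** Section 2 makes safety against vehicle the primary objective, and section 3.1 gives the measure: "The primary safety parameter in this study is the incidence and severity of treatment-emergent and treatment-related adverse events (AEs), both systemic and ocular events". The synopsis narrows this to ocular AEs. Four rules then bear on an eye whose inflammation worsens after study drops are started.

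- Section 3.1: "Changes that are expected due to uncomplicated cataract surgery will not be classified as AEs but will be recorded".
- Section 6.2: "Subjects on rescue will be considered treatment failures, but the need for rescue therapy will not be considered an AE". Section 6.3 defines rescue as "any treatment that would have a therapeutic effect on inflammation in the anterior segment, other than the IP". Under 6.2 a rescued subject stops study drops and is followed through Visit 6.
- Section 7.3 includes under the unrelated category: "Event easily explained by uncomplicated cataract surgery".
- Section 9.1.2 says that treatment-emergent AEs will be listed by group, while treatment-related AEs will be tabulated by group with their incidence. It also names slit-lamp biomicroscopy as a safety outcome, without saying which signs.

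The slit-lamp row of Table 4 (section 7.2) names "Lid hyperemia, lid edema, conjunctival hyperemia, chemosis, corneal edema, conjunctival discharge/exudate". Cells and flare are not in it. Where the analysis sections name them, it is as efficacy. Section 9.1.3: "Efficacy measures will be ACC and flare, as well as Subject-rated Ocular Pain Assessment", with cells and flare assessed as change from Day 1 on Days 3, 8 and 15.

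**The concern.** A new eye drop given to a freshly operated eye could itself provoke inflammation, and a dose-ranging safety study should be able to show that. Such an eye is also a likely candidate for stopping study drops and being rescued. If rescue is not counted as safety and the worsening is not separately recorded, the most affected subjects are those most easily absent from the primary comparison, and the shortfall grows with any real dose effect.

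Sites could also differ. One working from 3.1 and 6.2 may record a treatment failure and no AE. Another working from the general AE definition in 7.3 may record an AE for the same event. With about 60 subjects at about five centers, a few such differences can change what an arm appears to show.

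**Working it through.** **Following one eye through the text.** Suppose an eye enters at grade 2 cells, worsens on study drops and is rescued.

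1. Is the rescue an AE? No, under 6.2.
2. Is the worsening an AE? The text leaves this open. Section 7.3 would admit it as an untoward occurrence. Section 3.1 would exclude it if the investigator regards it as expected after surgery, and 3.1 sets no limit by grade or against Day 1. Section 1 supplies a reason to regard it so: "Intraocular inflammation is a typical undesirable consequence of intraocular surgery such as cataract surgery".
3. If an AE is recorded, is it tabulated? Under 9.1.2 only if judged related. The scale in 7.3 runs from unrelated to probable to definite with no level between unrelated and probable, and an event easily explained by surgery falls under unrelated.
4. Is the rescue counted elsewhere? It goes on the eCRF (6.3, 7.2.2), but neither 9.1.2 nor 9.1.3 has an output that uses rescue or treatment failure by arm.
5. Do the cell and flare scores show it? Only partly. The summaries in 9.1.3 use Days 3, 8 and 15. A peak seen at an unscheduled visit (5.1.7) falls outside them, and scores after rescue are taken on anti-inflammatory treatment, so they can look improved. A group summary of change also does not count the eyes that got worse.

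**Size.** The documents give no figure to reproduce; section 9.2 is redacted. About 60 subjects (3.3) allocated 1:1:1:1 (4.3.1) give 60/4 = 15 per arm. The rest is assumption. Let r be the proportion of an arm rescued for drug-provoked inflammation, and s the share of those eyes that reach the AE table, that is, the chance of being recorded times the chance of then being called related. For example, 0.5 × 0.5 = 0.25.

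- Expected rescued eyes = 15r
- Expected eyes in the AE table = 15rs
- Chance of at least one in the table = 1 − (1 − rs)^15

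| r | Rescued | s = 1 | s = 0.5 | s = 0.25 | s = 0 |
|---|---|---|---|---|---|
| 10% | 1.5 | 1.5 (0.794) | 0.75 (0.537) | 0.375 (0.316) | 0 (0) |
| 20% | 3.0 | 3.0 (0.965) | 1.5 (0.794) | 0.75 (0.537) | 0 (0) |
| 40% | 6.0 | 6.0 (1.000) | 3.0 (0.965) | 1.5 (0.794) | 0 (0) |

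Cells show the expected number in the table, with the chance of at least one in brackets.

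At the extreme s = 0, three rescued eyes would be shown as 0/15, with a one-sided 95% upper limit of 1 − 0.05^(1/15) = 18.1%. Counting rescue would show 3/15 = 20% (exact 95% interval 4.3% to 48.1%). A split of 6/15 against 0/15 rescued (two-sided Fisher p = 0.017, as a yardstick only) would appear as 0 against 0.

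**The case against.** The strongest answer is that 6.2 excludes the need for rescue, not the event behind it. The same section foresees a rescued subject who has an AE at that time, and the definition in 7.3 is wide. The examples of expected changes in 3.3 include corneal edema and discomfort but not rising cells or flare, and the line in section 1 is background, not an AE rule. All this stands. A reader might infer that the protocol removes worsening inflammation from the AEs by rule; it does not. It leaves the recording to the investigator.

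Nor do the documents support saying that cells and flare are handled only as efficacy. Slit-lamp biomicroscopy is a safety item in the synopsis, 3.1 and 9.1.2, and 8.1 includes cells and flare in that examination. Table 4 does not settle the matter, because it also omits visual acuity, which 3.1 and 9.1.2 name as safety. What remains is that no text says a rise in cells or flare will be counted by arm as safety.

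The data are not lost either. Rescue is recorded with indication and start date, all study data are listed by treatment, subject and visit (9.1), and rescued subjects stay in the Safety Population (9.6). Section 7.2.1 also promises separate summaries of ocular and non-ocular AEs without limiting them to related events, though it does not say by arm and differs from 9.1.2.

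Finally, the rescue criteria in 7.2.2 and the text after them are redacted, and 9.1 refers to a Statistical Analysis Plan of which no separate text is available here. Either could close the gap. That limits the point to what is visible.

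**Conclusion.** The point stands as a gap in specified safety reporting. On the visible text, a worsened and rescued eye reaches the tabulated AE comparison only if the investigator records a separate AE and judges it related. No by-arm count of rescue, or of worsening cells or flare, backs that up. Under the assumed 10% to 40% rates, 1.5 to 6 eyes per arm are at issue, and anything from none to all of them could appear.

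These figures rest on 15 per arm and on assumed rates; the documents give no rescue rate. It would be wrong to read 3/15 as a true count of harm. Section 1 puts resolution without treatment at 15% to 28%, so rescue for lack of effect is plausible in every arm, vehicle included. Only the difference from vehicle is informative.

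**What to change.** Add to 9.1.2, as descriptive safety outcomes by arm against vehicle:

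- the number of subjects rescued, with recorded reason and study day;
- the number with any increase in cells or flare over Day 1, at any scheduled or unscheduled visit up to rescue, or to the end of follow-up if not rescued.

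Tabulate all treatment-emergent AEs by arm, not only those judged related, and bring 9.1.2 and 7.2.1 into line.

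Ask the sponsor to reconcile 3.1, 6.2 and 7.3 on whether worsening above the subject's Day 1 grade is assessed as an AE, so that all sites apply the same reading. Which reading to adopt is a clinical classification for the sponsor, and none is proposed here. If the redacted text or the Statistical Analysis Plan already contains these outputs, a cross-reference from 9.1.2 is enough.

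The cost is a few descriptive rows from data already collected, with no change to care or visits. The drawback is that rescue for lack of effect will also appear, including on vehicle. The table should therefore carry a note that the counts are to be read against vehicle and not all as drug harm.
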